1. INTRODUCTION

The following analysis plan provides the framework for the summarization of the data from this study. The Statistical Analysis Plan (SAP) may change due to unforeseen circumstances. Any changes made after the unblinding or locking of the database will be documented in the clinical study report (CSR). Please note that the header for this page will be the one used for the main body of the CSR.

Any additional exploratory analyses not addressed within this SAP and/or driven by the data, or requested by Yungjin Pharm. CO., LTD., will be considered out of scope and must be approved, by Yungjin Pharm. CO., LTD., and must be described in the CSR.

2. OBJECTIVES AND ENDPOINTS

2.1 Objectives

Primary Objective: To assess the safety and tolerability of two multiple oral YPL-001 dose levels versus placebo in moderate to severe chronic obstructive pulmonary disease (COPD) patients.

Secondary Objective: To assess the number and magnitude of daily respiratory symptoms of two multiple oral YPL-001 dose levels versus placebo in moderate to severe COPD patients.

Exploratory Objectives: To evaluate the following in moderate to severe COPD patients:

1. To assess BAL epithelial brushings for YPL-001 component levels.
2. To compare BAL samples for total cell count (cells/mL) macrophages, lymphocytes, neutrophils, and eosinophils as a percentage of total cells; neutrophil, macrophage, lymphocyte, and eosinophil counts as absolute inflammatory cell numbers in YPL-001 groups versus placebo group.
3. To compare BAL samples for TNF- α , IL-1 β , IL-4, IL-5, IL-6, IL-8, IL-13, MPO, neutrophil elastase, MCP-1, and MMP-9 in YPL-001 groups versus placebo group.
4. To compare blood inflammatory markers (total and differential cell counts as absolute and percentage for neutrophils, monocytes, eosinophils and lymphocytes) and concentrations of CRP, fibrinogen, TNF- α , IL-1 β , IL-4, IL-5, IL-6, IL-8, IL-13, MCP-1, and MMP-9 in YPL-001 groups versus placebo group.
5. To compare spirometric functions (FEV₁, FVC, FEV₁/FVC, and IC) in YPL-001 groups versus placebo group.

6. To compare patient reported outcomes (BDI/TDI, CAT) in YPL-001 groups versus placebo group.
7. To assess verproside and picroside II concentration in plasma and BAL and verproside and picroside II PK in plasma following multiple oral doses administration of two YPL-001 dose levels.

2.2 Endpoints

Primary Endpoint: The number and severity of treatment-emergent adverse events (TEAEs) following multiple oral doses of YPL-001 or placebo.

Secondary Endpoint: The number of symptom free days and overall symptom burden following multiple oral doses of YPL-001 or placebo, assessed by measuring:

- daily peak expiratory flow (PEF);
- major (e.g., estimated sputum quality (e.g., color, consistency) and quantity) and minor (e.g., cough, wheeze, sore throat, nasal congestion, discharge, and body temperature above 100°F) symptoms of COPD exacerbation;
- dyspnea (using the Modified Borg Dyspnea Scale);
- activity (using the Duke Activity Status Index [DASI]).

Exploratory Endpoints:

1. YPL-001 component levels in epithelial brushings;
2. BAL biomarkers following multiple oral doses of YPL-001 or placebo, measuring:
 - total cell count (cells/mL) of macrophages, lymphocytes, neutrophils, and eosinophils as a percentage of total cells
 - total cell count (cells/mL) of neutrophils, macrophages, lymphocytes, and eosinophils as absolute inflammatory cell numbers
 - concentrations of TNF- α , IL-1 β , IL-4, IL-5, IL-6, IL-8, IL-13, MPO, neutrophil elastase, MCP-1, and MMP-9.
3. Blood biomarkers following multiple oral doses of YPL-001 or placebo, measuring:
 - inflammatory markers (total and differential cell counts as absolute and percentage for neutrophils, monocytes, eosinophils, and lymphocytes)

- concentrations of CRP, fibrinogen, TNF- α , IL-1 β , IL-4, IL-5, IL-6, IL-8, IL-13, MCP-1, and MMP-9.
- 4. Pulmonary function results (spirometry) following multiple oral doses of YPL-001 or placebo.
- 5. Quality of life scores using the BDI/TDI, CAT questionnaires.
- 6. Concentrations and PK of verproside and picroside II in plasma following multiple oral doses of YPL-001.
- 7. Concentrations of verproside and picroside II in BAL following multiple oral doses of YPL-001.

3. STUDY DESIGN

This is a Phase 2a, proof-of-concept, multicenter, randomized, double-blind, double-dummy, 3-treatment, parallel study, with low and high YPL-001 doses (80 mg and 160 mg twice daily [BID]) and a placebo control, in moderate to severe COPD male and female patients.

Sixty (60) patients will be enrolled and randomized into 3 treatment groups (20 patients per group). Patients will participate only once. An approximately equal number of current and ex-smokers will be enrolled in the study.

Screening of patients will occur within 14 days of Day 1 (inclusive) of the Run-in Period.

Following screening, eligible patients will discontinue non-permitted respiratory drugs and enter a 14 ± 2 days Run-in Period during which patients will be given albuterol taken on an as required basis and daily tiotropium 18 μ g to be administered at home. They will record their daily symptoms in an electronic diary (e-diary) throughout the Run-in Period.

Patients will return to the clinical research unit (CRU) in the morning of Day -3 to -1 for Check-in of the Treatment Period to confirm their eligibility and undergo Check-in scheduled study procedures. Patients will return to the CRU on the morning of Day 1 to be randomized and receive one of the 3 treatments and undergo all scheduled study procedures. Patients will return on the morning of Days 15 (± 2 days), 29 (± 2 days), 43 (± 2 days), 54 (± 1 day), and 56 of the Treatment Period for study drug administration and procedures. Prior to each release from the CRU, patients will receive sufficient doses to be self-administered at home until the next morning visit at the CRU. Patients will continue recording their daily symptoms via the e-diary throughout the Treatment Period.

YLP-001 and placebo will be administered approximately every 12 hours under fasting conditions.

Patients will remain ambulatory or seated upright for 1 hour following each study medication administration.

Safety and tolerability will be assessed throughout the study through physical examinations, vital signs, pulse oximetry, electrocardiograms (ECGs), clinical laboratory tests, and adverse events (AEs).

Assessment of respiratory symptoms and symptom burden in YPL-001 and placebo treatments will be performed daily through patient self-report of PEF, major and minor symptoms of COPD exacerbation, dyspnea, and activity.

Spirometry measurement, quality of life assessments, BAL, and blood samples will be collected for the pharmacodynamic (PD) assessment of YPL-001 and placebo treatments.

Serial blood samples will also be collected for PK assessment of verproside and picroside II in plasma and BAL.

The CRU will attempt to contact patients using their standard procedures approximately 14 days after the last study drug administration to determine if any AE has occurred since the last dose of study drug.

The planned length of participation in the study for each patient is approximately 12 weeks (from Run-in through follow-up).

4. ANALYSIS POPULATIONS

4.1 Analysis Populations

Safety population: All available data for patients who received at least one dose of the investigational product (i.e., YPL-001) or placebo. Safety data for all discontinued patients will be included in this set for the time points for which their data are available.

Symptom monitoring population: All available data for patients who received at least one dose of the investigational product (i.e., YPL-001) or placebo. Symptom monitoring data for all discontinued patients will be included in this set for the time points for which their data are available.

PK population: All patients receiving at least one dose of YPL-001 and having at least one measurable plasma concentration of verproside and picroside II.

PK per-protocol population: All protocol-compliant patients who received all scheduled doses of YPL-001 and have sufficient samples collected to determine PK parameters from plasma concentrations of verproside and picroside II on at least one of the two PK days (Days 1 and 54 (± 1 day) or 56).

PD population: All patients who received at least one dose of YPL-001 or placebo and provide at least one post-baseline PD measurement.

PD per-protocol population: All protocol-compliant patients who received all scheduled doses of YPL-001 or placebo and have measurable PD data.

PK/PD population: All patients who received at least one dose of YPL-001 and having any measurable concentration of verproside and picroside II and measurable PD data will be included in the PK/PD relationship assessment, as applicable.

4.2 Preliminary Data and Interim Analysis

No formal interim analysis is planned for this study.

5. TREATMENT DESCRIPTIONS

5.1 Study Treatments

YPL-001 will be supplied as 80 mg tablets for oral administration.

Placebo will be supplied as YPL-001 80 mg matching placebo tablets for oral administration.

Treatments A, B, and C are described as follows:

Treatment A: Multiple oral YPL-001 80 mg doses (1 x 80 mg tablet + 1 x 1 YPL-001 80 mg matching placebo tablet) will be administered approximately every 12 hours under fasting conditions for 55 consecutive days.*

Treatment B: Multiple oral YPL-001 160 mg doses (2 x 80 mg tablets) will be administered approximately every 12 hours under fasting conditions for 55 consecutive days.*

Treatment C: Multiple oral matching placebo (2 x 1 YPL-001 80 mg matching placebo tablets) will be administered approximately every 12 hours under fasting conditions for 55 consecutive days.*

* Patients following up to Amendment version 5 of protocol also received a morning dose on Day 56

In the tables, figures, and listings (TFLs) (PK, PD, and safety), treatments will be referred to as:

Treatment A: Multiple oral doses of YPL-001 80 mg BID on Days 1 – 55.

Treatment B: Multiple oral doses of YPL-001 160 mg BID on Days 1 – 55.

Treatment C: Multiple oral doses of placebo BID on Days 1 – 55.

Note: Patients following up to Amendment version 5 of the protocol also received a morning dose on Day 56.

In the text of the CSR, treatments will be referred to as Treatments A, B and C or as 80 mg YPL-001, 160 mg YPL-001, and placebo, respectively.

The finished product will be referred to in the CSR as YPL-001 or placebo. The active ingredient will be referred to in the CSR as verproside and picroside II.

5.2 Other Treatments

Tiotropium (Spiriva® HandiHaler®) will be supplied as 18 µg capsules for inhalation.

Albuterol will be supplied as 100 µg albuterol base (1 actuation = 100 µg albuterol base) for oral inhalation. Albuterol may be administered via a nebulizer or a metered-dose inhaler.

During the Run-in Period, multiple oral inhalation of tiotropium (Spiriva® HandiHaler®) 18 µg capsule will be administered QD every morning for 14 ± 2 days. Albuterol will be administered on an as needed basis.

In treatments A to C, one tiotropium (Spiriva® HandiHaler®) 18 µg capsule will also be administered QD every morning prior to study drugs administration. Albuterol will be administered on an as needed basis.

6. SYMPTOM MONITORING ANALYSIS

The following section is organized based on the secondary endpoints in [Section 2.2](#).

6.1 Measurements, Collection Schedule, and Analysis

When readings are not performed in the CRU, patients will record their daily symptoms in their e-diary prior to each dose from Day 1 of the Run-in Period through the Treatment Period. Patients will return the e-diary device on Day 56 (or prior to early termination) to CRU.

The following symptoms will be monitored daily by all patients:

Peak Expiratory Flow: Three (3) PEF measurements will be made at each time point. PEF measurements and their change from baseline will be summarized by treatment and time point of collection. Baseline is Day 1 predose measurement.

Symptoms of COPD Exacerbation: Major (estimated sputum quality [color and consistency] and quantity) and minor (cough, wheeze, sore throat, nasal congestion, nasal discharge, and body temperature above 100°F) symptoms of COPD exacerbation and their change from baseline will be listed and presented descriptively. Baseline is Day 1 predose measurement.

Dyspnea: Severity level of patient's dyspnea will be assessed via the Modified Borg Dyspnea Scale (0 to 10; where 0 corresponds the absence sensation of dyspnea and 10 corresponds to maximum possible sensation of dyspnea). The Modified Borg Dyspnea Scale scores will be listed and presented descriptively.

Activity: Patient's functional capacity and activity status will be assessed via the DASI 12-item questionnaire. The final score ranges between 0 and 58.2 points. The higher the score, the better the functional capacity. DASI scores will be listed and presented descriptively.

Additional analysis may be performed if deemed appropriate.

6.2 Data Summarization and Presentation

Symptom free days and overall symptom burden will be evaluated and compared across treatment groups. Secondary outcome analysis will be based on treatment actually received by patients. Quantitative data will be summarized by treatment group using descriptive statistics including sample size (N), arithmetic mean, standard deviation (SD), coefficient of variation (CV%), median, minimum, and maximum. Frequency counts will be compiled for classification of qualitative data, when appropriate. Descriptive statistics and frequency counts will be generated using SAS® Version 9.3 (or higher).

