12.1 In-text Table Shells

Note to programmer: Formatting and content of PK and PD in-text tables may be modified based on provided data.

Table 10-1 Disposition Summary by Treatment

Disposition	Treatment A YPL-001 80 mg	Treatment B YPL-001 160 mg	Treatment C Placebo	Total
Dosed	XX (100%)	XX (100%)	XX (100%)	XX (100%)
Completed Study	XX (XX%)	XX (XX%)	XX (XX%)	XX (XX%)
Dropped from Study	XX (XX%)	XX (XX%)	XX (XX%)	XX (XX%)
Adverse Event	X (X%)	X (X%)	X (X%)	X (X%)
Protocol Deviation	X (X%)	X (X%)	X (X%)	X (X%)
Other	X (X%)	X (X%)	X (X%)	X (X%)
Etc.	X (X%)	X (X%)	X (X%)	X (X%)

Percentage is based on number of patients dosed in a given dose.

Treatment A: Multiple oral doses of YPL-001 80 mg BID on Days 1 – 55
Treatment B: Multiple oral doses of YPL-001 160 mg BID on Days 1 – 55
Treatment C: Multiple oral doses of placebo BID on Days 1 – 55
Note: Patients following up to Amendment version 5 of the protocol also received a morning dose on Day 56.

Source: Table 14.1.1 and Appendix 16.2.1

Table 11-1 Summary and Change From Baseline of Main Peak Expiratory Flow (PEF) Recorded in the e-Diary Following Multiple Oral YPL-001 Doses of 80 mg and 160 mg and Placebo in COPD Patients

Day	Main Peak Expiratory Flow (L/min)					
	Treatment A YPL-001 80 mg		Treatment B YPL-001 160 mg		Treatment C Placebo	
	Result	Change from Baseline	Result	Change from Baseline	Result	Change from Baseline
1	XXX± XXX (N=X)	NA	XXX± XXX (N=X)	NA	XXX± XXX (N=X)	NA
2	XXX± XXX (N=X)	XXX± XXX (N=X)	XXX± XXX (N=X)	XXX± XXX (N=X)	XXX± XXX (N=X)	XXX± XXX (N=X)
3	XXX± XXX (N=X)	XXX± XXX (N=X)	XXX± XXX (N=X)	XXX± XXX (N=X)	XXX± XXX (N=X)	XXX± XXX (N=X)
4	XXX± XXX (N=X)	XXX± XXX (N=X)	XXX± XXX (N=X)	XXX± XXX (N=X)	XXX± XXX (N=X)	XXX± XXX (N=X)
5	XXX± XXX (N=X)	XXX± XXX (N=X)	XXX± XXX (N=X)	XXX± XXX (N=X)	XXX± XXX (N=X)	XXX± XXX (N=X)
<>	XXX± XXX (N=X)	XXX± XXX (N=X)	XXX± XXX (N=X)	XXX± XXX (N=X)	XXX± XXX (N=X)	XXX± XXX (N=X)

Presented as arithmetic mean ± SD, baseline is Day 1.

Treatment A: Multiple oral doses of YPL-001 80 mg BID on Days 1 – 55

Treatment B: Multiple oral doses of YPL-001 160 mg BID on Days 1 – 55

Treatment C: Multiple oral doses of placebo BID on Days 1 – 55

Note: Patients following up to Amendment version 5 of the protocol also received a morning dose on Day 56.

Source: Table 14.2.1.1

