4 PM	X (%)	X (%)	X (%)
5 AM	X (%)	X (%)	X (%)
5 PM	X (%)	X (%)	X (%)
6 AM	X (%)	X (%)	X (%)
6 PM	X (%)	X (%)	X (%)
7 AM	X (%)	X (%)	X (%)
7 PM	X (%)	X (%)	X (%)
8 AM	X (%)	X (%)	X (%)
8 PM	X (%)	X (%)	X (%)
9 AM	X (%)	X (%)	X (%)
9 PM	X (%)	X (%)	X (%)
10 AM	X (%)	X (%)	X (%)
10 PM	X (%)	X (%)	X (%)
< >	< >	< >	< >

Number of subjects dosed by day with percentage is based on total number of subjects dosed in each treatment.

Treatment A: Multiple oral doses of YPL-001 80 mg BID on Days 1 - 55

Treatment B: Multiple oral doses of YPL-001 160 mg BID on Days 1 - 55

Treatment C: Multiple oral doses of placebo BID on Days 1 - 55

Note: Patients following up to Amendment version 5 of the protocol also received a morning dose on Day 56.

Program : /AAXXXX/ECR/sas_prg/stsas/tab/PROGRAMNAME.sas DDMMYYYY HH:MM

Symptom Monitoring

Page X of X

Table 14.2.1.1 Summary and Change From Baseline of Main Peak Expiratory Flow (PEF) Recorded in the e-Diary Following Multiple Oral YPL-001 Doses of 80 mg and 160 mg and Placebo in COPD Patients (Treatments A - C)

Day	Summary Statistic	Treatment A		Treatment B		Treatment C	
		Result (N = XX)	Change From Baseline (N = XX)	Result (N = XX)	Change From Baseline (N = XX)	Result (N = XX)	Change From Baseline (N = XX)
1	N	XX		XX		XX	
	Mean	XX.X		XX.X		XX.X	
	SD	XX.XX		XX.XX		XX.XX	
	CV%	XX.X		XX.X		XX.X	
	Median	XX.X		XX.X		XX.X	
	Minimum	XX		XX		XX	
	Maximum	XX		XX		XX	
2	N	XX	XX	XX	XX	XX	XX
	Mean	XX.X	-X.X	XX.X	-X.X	XX.X	-X.X
	SD	XX.XX	XX.XX	XX.XX	XX.XX	XX.XX	XX.XX
	CV%	XX.X	XX.X	XX.X	XX.X	XX.X	XX.X
	Median	XX.X	-X.X	XX.X	-X.X	XX.X	-X.X
	Minimum	XX	-XX	XX	-XX	XX	-XX
	Maximum	XX	XX	XX	XX	XX	XX
	P-Value (Within)		X.XXX		X.XXX		X.XXX
	P-Value (Between)		X.XXX		X.XXX		X.XXX

Main peak expiratory flow (L/min) = Highest of the three peak flow recordings
 Baseline is Day 1 predose measurement.

P-value (Within) came from Wilcoxon Signed Rank Test, P-value (Between) came from Wilcoxon Rank Sum Test: A vs C and B vs C

Treatment A: Multiple oral doses of YPL-001 80 mg BID on Days 1 - 55

Treatment B: Multiple oral doses of YPL-001 160 mg BID on Days 1 - 55

Treatment C: Multiple oral doses of placebo BID on Days 1 - 55

Note: Patients following up to Amendment version 5 of the protocol also received a morning dose on Day 56.

Program : /AAXXXX/ECR/sas_prg/stsas/tab/PROGRAMNAME.sas DDMMYYYY HH:MM

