		Result (N = XX)	Change From Baseline (N = XX)	Result (N = XX)	Change From Baseline (N = XX)	Result (N = XX)	Change From Baseline (N = XX)
1	N	XX		XX		XX	
	Mean	XX.X		XX.X		XX.X	
	SD	XX.XX		XX.XX		XX.XX	
	CV%	XX.X		XX.X		XX.X	
	Median	XX.X		XX.X		XX.X	
	Minimum	XX		XX		XX	
	Maximum	XX		XX		XX	
2	N	XX	XX	XX	XX	XX	XX
	Mean	XX.X	-X.X	XX.X	-X.X	XX.X	-X.X
	SD	XX.XX	XX.XX	XX.XX	XX.XX	XX.XX	XX.XX
	CV%	XX.X	XX.X	XX.X	XX.X	XX.X	XX.X
	Median	XX.X	-X.X	XX.X	-X.X	XX.X	-X.X
	Minimum	XX	-XX	XX	-XX	XX	-XX
	Maximum	XX	XX	XX	XX	XX	XX
	P-Value (Within)		X.XXX		X.XXX		X.XXX
	P-Value (Between)		X.XXX		X.XXX		X.XXX

Baseline is Day 1 predose measurement.

P-value (Within) came from Wilcoxon Signed Rank Test, P-value (Between) came from Wilcoxon Rank Sum Test: A vs C and B vs C
 Modified Borg Dyspnea Scale: 0 = None, 0.5 = Very Mild, 1 = Less Mild, 2 = Mild, 3 = More Mild, 4 = Less Moderate, 5 = Moderate,
 6 = More Moderate, 7 = Less Severe, 8 = Severe, 9 = More Severe, 10 = Extreme

Treatment A: Multiple oral doses of YPL-001 80 mg BID on Days 1 - 55

Treatment B: Multiple oral doses of YPL-001 160 mg BID on Days 1 - 55

Treatment C: Multiple oral doses of placebo BID on Days 1 - 55

Note: Patients following up to Amendment version 5 of the protocol also received a morning dose on Day 56.

Program : /AAXXXX/ECR/sas_prg/stsas/tab/PROGRAMNAME.sas DDMMYYYY HH:MM

Table 14.2.1.8 Categorical Summary of 12-Item Questionnaire of Duke Activity Status Index (DASI) Recorded in the e-Diary Following Multiple Oral YPL-001 Doses of 80 mg and 160 mg and Placebo in COPD Patients (Treatments A - C)

		DASI 12-Item Questionnaire												
Day	Treat- ment	N	1	2	3	4	5	6	7	8	9	10	11	12
1	A	XX	XX (XX%)	XX (XX%)	XX (XX%)	X (X%)	X (X%)	X (X%)	X (X%)	XX (XX%)	XX (XX%)	X (X%)	X (X%)	X (X%)
	B	XX	X (XX%)	X (XX%)	X (XX%)	X (X%)	X (XX%)	X (XX%)	X (X%)	X (X%)	X (XX%)	X (X%)	X (X%)	X (X%)
	C	XX	X (XX%)	X (XX%)	X (XX%)	X (X%)	X (X%)	X (X%)	X (X%)					
2	A	XX	XX (XX%)	X (X%)	X (X%)	XX (XX%)	XX (XX%)	XX (XX%)	X (X%)	X (X%)	X (X%)	X (X%)	X (X%)	X (X%)
	B	XX	X (XX%)	X (XX%)	X (XX%)	X (X%)	X (X%)	X (X%)	X (X%)					
	C	XX	XX (XX%)	X (X%)	X (X%)	XX (XX%)	X (X%)	X (X%)	X (X%)	X (X%)				

< >

1. Able to take care of yourself that is eating, dressing, bathing, or using the toilet yet?
2. Able to walk indoors, such as around the house?
3. Able to walk a block or 2 on level ground?
4. Able to climb a flight of stairs or walk up a hill without stopping?
5. Able to run a short distance?

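### The only secondary endpoint, symptom-free days and overall symptom burden, is promised an across-arm comparison, but no listed output forms either quantity per patient, and the only between-arm tests are daily p-values that Section 6 does not describe

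*SAP*

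**What the plan says.** Section 2.2 gives a single secondary endpoint: "The number of symptom free days and overall symptom burden following multiple oral doses of YPL-001 or placebo, assessed by measuring" four things, namely daily peak expiratory flow (PEF), major and minor exacerbation symptoms, dyspnea on the Modified Borg scale, and activity on the DASI. Section 6.2 then commits to an analysis: "Symptom free days and overall symptom burden will be evaluated and compared across treatment groups". The only methods it names are summary statistics by arm and frequency counts. Section 6.1 is similar. For dyspnea, for example: "The Modified Borg Dyspnea Scale scores will be listed and presented descriptively". The DASI is treated the same way.

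The listed symptom outputs are in-text Tables 11-1 to 11-5, Tables 14.2.1.1 to 14.2.1.9, and Appendices 16.2.6.1.1 to 16.2.6.1.4. The tables have one row or block per study day, and the appendices one row per assessment.

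Four Section 14 shells go further than Section 6. Tables 14.2.1.1 (PEF), 14.2.1.5 (symptom score), 14.2.1.7 (Borg) and 14.2.1.9 (DASI) carry p-value rows under change from baseline, with the footnote: "P-value (Within) came from Wilcoxon Signed Rank Test, P-value (Between) came from Wilcoxon Rank Sum Test: A vs C and B vs C". The matching in-text shells carry none. The note under Table 11-1 reads only: "Presented as arithmetic mean ± SD, baseline is Day 1".

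**The concern.** An endpoint defined over the treatment period needs one value per patient before arms can be compared. Run as written, the plan yields a long sequence of daily summaries and daily tests, and no estimate of the endpoint it names. The SAP also leaves open which components make a day symptom-free, what cut-off applies on the symptom score, how unrecorded days count, and how twice-daily entries become one day. Unless the protocol settles these, they could be decided after the data have been seen.

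Separately, the shells and Section 6 disagree on whether symptom data are tested at all. A reader of Section 14 could over-read an isolated small p-value on one day.

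**Working it through.** **1. Is either quantity formed anywhere?**

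- PEF: Tables 11-1 and 14.2.1.1, by day.
- Sputum and minor symptoms: Tables 11-2.1 to 11-2.3, 14.2.1.2 and 14.2.1.3, by day.
- Symptom score (0 to 3.5): Tables 11-3.1, 11-3.2, 14.2.1.4 and 14.2.1.5, by day.
- Borg: Tables 11-4, 14.2.1.6 and 14.2.1.7, by day.
- DASI: Tables 11-5, 14.2.1.8 and 14.2.1.9, by day.
- Appendices 16.2.6.1.1 to 16.2.6.1.4: by patient and assessment, with no total over days.

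The nearest approach is Table 14.2.1.4, which gives each arm's daily count at each score. With complete diaries, summing the counts at the qualifying scores over days and dividing by the number of patients gives an arm mean number of days free on the symptom score. It gives no spread, no interval and no missing-day rule, and it covers only one of the four components. The shell's Normal band spans 0 to 0.5, so even there the cut-off is not fixed.

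**2. How many between-arm tests do the shells imply?** The SAP states no count, so there is no figure to reproduce. Inputs:

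- Tables with a between-arm p-value: 4 (Section 12.2).
- Contrasts: 2, A versus C and B versus C (footnote).
- Post-baseline days: dosing on Days 1 to 55 (Section 5.1) with Day 1 predose as baseline (Section 6.1), so 55 - 1 = 54.

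Between-arm tests: 4 x 54 x 2 = 432. Expected number below an assumed two-sided 0.05 with no effect: 432 x 0.05 = 21.6, about 22. That expectation holds whatever the correlation between days. Within-arm signed-rank tests add 4 x 54 x 3 = 648.

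The count is conditional. The four shells show only Days 1 and 2. The in-text tables that name them as source show Days 1 to 5 and a continuation row, so later days are clearly intended, but the SAP does not say that every day carries a p-value. Including Day 56 gives 4 x 55 x 2 = 440. Testing two entries a day would give 432 x 2 = 864. The four shells also print a between-arm p-value under Treatment C, although the footnote names only two contrasts; 432 follows the footnote.

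**3. Does the missing-day rule matter?** Take a patient who stops after Day 28, symptom-free on all of Days 2 to 28:

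- Count of symptom-free days: 28 - 1 = 27.
- Proportion of recorded days: 27/27 = 100%.
- Proportion of the 54-day window: 27/54 = 50%.

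In an arm of 20 (Section 3), scoring that one patient 27 rather than 54 days moves the arm mean by (54 - 27)/20 = 1.35 days.

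**4. One entry a day or two?** Section 6.1 has diary entries made before each dose, and dosing is twice daily. The same section calls the monitoring daily, and the shells have one row per day. No rule links them.

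**The case against.** The strongest reply is that definitions may sit in the protocol, which is not to hand. The 0 to 3.5 score and its severity bands presuppose a scoring rule held somewhere, and a symptom-free day may be defined with it. That stands. A reader might infer that the trial has no definition and that the sponsor is free to choose one late, but the SAP alone cannot show that. A protocol definition would still not supply the output that Section 6.2 promises and the SAP omits, nor reconcile the shells with Section 6.

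Second, the table lists and shells are declared open to modification (Sections 11.2 and 12), and Section 6.1 allows additional analysis. This softens the gap without closing it: an output added later for the only secondary endpoint is an unplanned derivation.

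Third, this is a small phase 2a trial with a mainly descriptive plan. That is fair, and a reader might take the 432 tests as an uncontrolled error rate for a trial claim. The documents do not support that reading. No success rule uses these p-values, in-text Tables 11-1 to 11-5 leave them out, and the number itself extrapolates from shells showing two days. Yet the SAP is explicit elsewhere about what it intends: Section 8.7 gives model code and a 90% interval for an exploratory PK comparison, and Section 10 rules out inference for safety. The secondary endpoint gets neither.

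Fourth, nothing shows that a single composite was intended. Section 2.2 lists four measures and Section 6.1 reports them separately. That also stands. The scales differ (L/min, 0 to 3.5, 0 to 10, 0 to 58.2), and higher is better on PEF and DASI but worse on the other two. The absence of a composite is therefore not itself an error, and inventing one now would be worse.

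**Conclusion.** The point holds and should be fixed before unblinding. The SAP promises an across-arm comparison of its only secondary endpoint and lists no output that forms either quantity per patient. The only symptom-data inference it contains is unadjusted, daily, confined to four shells, and inconsistent with a section limited to descriptive statistics and frequency counts.

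The size is moderate. The missing estimate is the main loss. The 432 tests, with about 22 nominally significant under no effect, rest on one row per day for Days 2 to 55 and an assumed 0.05. They are a risk of over-reading, not a threat to a prespecified claim. Whether the definitions are missing from the trial, rather than from this document, cannot be settled without the protocol.

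**What to change.** Before unblinding:

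1. Define a symptom-free day: which of the four components decide it, and whether a symptom score of 0, or 0 to 0.5, qualifies. If the protocol defines it, cite that. Report burden as the separate component means unless a composite is already defined.
2. Reconcile entries before each dose with daily monitoring and the one-row-per-day shells. If there are two entries a day, choose a day-level rule that does not favour days with a missing entry, for instance always using the same scheduled entry, or treating a day as recorded only when both are present.
3. Per patient, over a fixed window such as Days 2 to 55, compute the proportion of symptom-free days among recorded days (multiplied by 54 if a number of days is wanted) and the mean burden. Add a sensitivity analysis counting unrecorded days as not symptom-free.
4. Add one table of A-versus-C and B-versus-C estimates with 95% confidence intervals, naming the interval method, since a proportion is bounded and arms have 20 patients. Where a baseline is needed, keep the stated Day 1 predose value; a run-in diary mean can serve as a sensitivity analysis only. With separate burden components this is (1 + 4) x 2 = 10 comparisons, or (1 + 1) x 2 = 4 with an existing composite.
5. Remove the daily p-values or label them exploratory, so that the shells and Section 6 agree, and settle the extra value printed under Treatment C.

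The cost is SAP text, one derived dataset and one table; the diary data are already being collected. The real downside is dilution of a late effect. If an effect grows linearly from zero on Day 1, the mean over Days 2 to 55 is (1 + 2 + ... + 54)/(54 x 54) = 55/108, about 51% of the Day 55 effect. The daily descriptive tables would still show that pattern.
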